**Post-operative care:**

- All patients will receive postoperative instructions, in case of moderate and severe pain, patients will be allowed to take Ibuprofen (400mg), and instructed to record number of Ibuprofen tablets.

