### **- Secondary objective:**

The secondary objective is to assess the incidence and severity of postoperative pain after root canal treatment using either Nano-chitosan, CHX, Chitosan/CHX combination or NaOCl as a final flush before obturation.

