##### **- Preoperative measures (for all groups):**

- Medical and dental history will be obtained from all patients participating in this research. Clinical and radiographic evaluation for each tooth included in this study will be recorded.
- Pain scale chart will be given to each patient to rate his /her pain level before endodontic treatment as preoperative reading on an NRS scale.
- Tooth will be anaesthetized using 1.8 ml Mepivacaine HCl 2% - Levonordefrin 1:20000 (Carpule Mepecaine-L, Alexandria Company for Pharmaceuticals and Chemical Industries, Egypt).
- The tooth will be isolated with rubber dam to maintain aseptic field, after isolation the tooth and surrounding field will be disinfected by a protocol using 3% hydrogen peroxide 2.5% sodium Hypochlorite before and after coronal access cavity preparation.
- The initial sample S1 will be collected from root canals before preparation using sterile # 15 paper points.

- Sterile saline solution will be injected in the canals followed by the insertion of a #15 K-file (Mani, Japan) to at least 1 mm short of the apex as confirmed by apex locator (Root ZX, J.Morita USA, Irvine, CA) to facilitate the insertion of the paper points to collect the samples.
- Each paper point will remain in place for at least 1 minute then immediately placed in test tubes containing reduced transport fluid and sent to the Microbiology Laboratory, Faculty of Medicine, Cairo University for microbiologic processing.
- Root canals will be mechanically prepared in a crown-down approach using the rotary files (M-Pro file system) in an endodontic motor (X-Smart, Dentsply Maillefer, USA) according to the manufacture instructions.

The following sequence will be used for all groups:

- # 18 file taper (orifice opener) 0.09 will be used to prepare two thirds of estimated working length.
- # 20 file taper 0.04 will used to full working length.
- #25 file taper 0.06 will used to full working length.
- #35file taper 0.04 will used to full working length.
- The canals will be thoroughly irrigated for 1 minute between every two subsequent files using 2 ml of 2.5% NaOCl.
- After complete preparation all canals will be flushed with EDTA followed by sterile saline.
- **Intervention for test group A**
  - After complete preparation, the canals will be flushed using 5 ml of Nano chitosan (Nano tech, Egypt) in a plastic syringe using Navitip needles (Ultradent, South Jordan,UT).

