**Secondary outcome:**

- **Postoperative pain:** will be recorded on a Numerical Rating scale (NRS), pain intensity will be recorded preoperatively and postoperatively after 6, 12, 24, 48, 72 hours and 7 days. The NRS consists of a 10-cm line anchored by two extremes "No pain" and "pain as bad as could be", patient will be asked to choose the mark that represent their level of pain. Pain level will be assigned to one of 4 categorical scores: **1**, None(0); **2**, Mild(1-3); **3**, Moderate(4-6); **4**, Severe (7-10).

Outcome	Tool	Unit	Time
Postoperative pain	Numerical rating scale NRS 	Categorial data	Immediately after treatment and Up to 7 days after endodontic treatment

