#### **20. Statistical methods:**

- Data will be analyzed using IBM SPSS advanced statistics (Statistical Package for Social Sciences), version 21 (SPSS Inc., Chicago, IL). Numerical data will be described as mean and standard deviation or median and range. Data will be explored for normality using Kolmogrov-Smirnov test and Shapiro-Wilk test. Comparisons between 4 groups for normally distributed numeric variables will be done using the ANOVA while for nonnormally distributed numeric variables will be done by Kruskal Wallis test. A p-value less than or equal to 0.05 will be considered statistically significant. All tests will be two tailed.
- Categorical data will be described as numbers and percentages and comparisons will be done by chi square test or fisher exact as appropriate

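### Rescue ibuprofen is counted but given no named role in the pain analysis, and no rule covers pain ratings made after a tablet, so absolute differences in pain between arms may be understated

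*Combined protocol and SAP*

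**What the plan says.** The secondary objective (section 7) is "to assess the incidence and severity of postoperative pain after root canal treatment" by irrigant. Section 12 fixes the readings: "pain intensity will be recorded preoperatively and postoperatively after 6, 12, 24, 48, 72 hours and 7 days". It then converts the score: "Pain level will be assigned to one of 4 categorical scores", with moderate starting at 4 and severe at 7.

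Rescue is described once, in section 11 under Post-operative care. For moderate and severe pain, "patients will be allowed to take Ibuprofen (400mg), and instructed to record number of Ibuprofen tablets". Only the number of tablets is asked for, not the time of intake.

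The tablet count does not appear among the outcomes (section 12), in the participant timeline (section 13) or among the data collection methods (section 18). The adherence reminders in section 11.b concern the recording of pain levels only.

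Section 20 is written by type of data. For categories: "Categorical data will be described as numbers and percentages and comparisons will be done by chi square test or fisher exact as appropriate". For numeric data: "Comparisons between 4 groups for normally distributed numeric variables will be done using the ANOVA", with Kruskal-Wallis if normality fails. It does not mention ibuprofen, ratings made after a tablet, or any covariate. The "preoperative reading on an NRS scale" taken before treatment has no stated role in adjustment.

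**The concern.** Rescue is permitted at the same two categories, moderate and severe, that count as a worse pain outcome. If one irrigant causes more pain, its patients would be expected to take more ibuprofen, and more of their later ratings could be pulled below 4. A patient can also reach moderate pain between two scheduled readings, take a tablet, and score mild at the next one; that episode would then be missing from the recorded incidence.

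The problem statement in section 6 hopes for irrigants less irritating to the periapical tissues than sodium hypochlorite. A pain comparison that is compressed by rescue leans towards no difference on that question. Without ibuprofen use shown by arm, a reader could not tell similar pain from unequal analgesic use.

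**Working it through.** **The plan's own figure.** No sample size or event rate is given for pain. The only calculation (section 14) is for bacterial count: difference 75, SD 75, 80% power, two-sided 5%. The normal approximation gives 2 × (1.96 + 0.84)² × (75/75)² = 15.7, so 16 per group. The t-test version gives 16.7, so 17, as stated. Then 17/0.85 = 20. The figure reproduces and is not in dispute; 20 per arm, with no losses, is used below.

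**Assumptions, none of them in the documents.**
- Moderate or severe pain at a reading without ibuprofen: 40% in one arm, 20% in another.
- Share of those patients who take ibuprofen: 50% to 75%.
- Share of takers whose next rating falls below 4: 50% to 70%.
- Uptake and relief are the same in both arms.

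**Formula.** Observed rate = rate without ibuprofen × (1 − uptake × relief).
- Low end: 1 − 0.50 × 0.50 = 0.75.
- High end: 1 − 0.75 × 0.70 = 0.475.

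| Masking | Worse arm | Other arm | Difference | Ratio | Fisher exact power, 20 per arm |
|---|---|---|---|---|---|
| None | 40% | 20% | 20 points | 2.0 | 19% |
| Low (× 0.75) | 30% | 15% | 15 points | 2.0 | 12% |
| High (× 0.475) | 19% | 9.5% | 9.5 points | 2.0 | 7% |

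The worse arm loses 10 to 21 points and the other arm 5 to 10.5. The masking is therefore larger in the worse arm in absolute points, but proportionally equal. The ratio stays at 2.0 and the order of the arms is kept.

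**A larger assumed contrast.** With 60% versus 20%:
- no masking: 40 points, Fisher power 65%;
- a quarter of moderate or severe ratings masked: 45% versus 15%, 30 points, power 44%;
- half masked: 30% versus 10%, 20 points, power 24%.

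**Sparse data, relevant to the remedy.** With 20 per arm and four arms, the probability that at least one arm has no events at a given reading is 1 − (1 − (1 − p)²⁰)⁴. At p = 5%, 0.95²⁰ = 0.358 and the result is 1 − 0.642⁴ = 83%. At p = 10%, 0.90²⁰ = 0.122 and the result is 1 − 0.878⁴ = 40%. Ordinary logistic regression at each reading would often fail.

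**The case against.** Section 20 is generic. It names neither CFU nor pain, and a recorded tablet count would fit its rule for numeric variables. A reader might infer that the tablets and the preoperative score are never analysed, but the text does not go that far. What stands is that the count is not named, that the preoperative score is not named for adjustment, and that a separate test on tablets would still leave the pain categories uncorrected. Nor does the plan say that ratings after ibuprofen are taken as reported; this follows only because no other rule is given.

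A reader might also infer that every patient who takes ibuprofen is next recorded as having no or mild pain. The documents do not support this. A moderate or severe rating at a scheduled reading still counts unless ibuprofen came before it, and relief need not be complete. From 12 hours on, the gaps between readings run from 12 to 96 hours, and nothing in the plan supports one masking factor across all of them.

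The trial was sized for bacterial count. In the 40% versus 20% illustration, power is only 19% with no masking, so a null pain result is likely with or without ibuprofen. This is fair: rescue is not the main reason such a result might occur. It remains a reason why the result could not be interpreted.

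Finally, pain experienced with rescue available is a legitimate question. That is also fair; the gap is that the plan does not say which question it is asking.

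**Conclusion.** The concern holds as a gap in the analysis of a secondary outcome. Ratings made after ibuprofen may be lowered, in absolute terms more often in an arm with more pain, and the plan has neither a rule for them nor a named comparison of rescue use. The consequence is a smaller absolute difference and less power.

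It is tempting to conclude that the worst arm would look the same as the others. The arithmetic does not show that: with equal uptake and relief the ratio stays at 2.0 and the ranking is unchanged. Only complete masking would make the arms alike, and nothing in the documents suggests it.

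The illustrated fall from 20 points to 15-9.5 points rests entirely on assumed pain rates, uptake and relief; the true size cannot be known from the documents. The primary outcome is untouched, because sample S2 is taken before obturation and so before any postoperative ibuprofen. The change is worth making because it is cheap and mostly uses data already being collected.

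**What to change.** Add one paragraph to section 20:

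- **Rescue use by arm.** Compare any ibuprofen use (Fisher exact) and tablet count (Kruskal-Wallis) across the four arms, reported beside the pain categories.
- **One patient-level composite.** Any postoperative NRS of 4 or more, or any ibuprofen, up to 7 days, compared by Fisher exact. Under the plan's own condition for taking it, ibuprofen already implies moderate or severe pain. A single composite per patient avoids counting one episode at two successive readings and needs no tablet times.
- **Supportive adjustment.** Where event numbers allow, adjust the composite for preoperative NRS with a sparse-data method such as Firth logistic regression.
- **Keep the as-reported categories** at each time, and say which question each analysis answers.

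Name the tablet count in sections 12 and 18, and add a time column for tablets to the existing paper chart, so that ratings can be classed as before or after ibuprofen. This column has to be in place before patients fill in the chart.

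The cost is a paragraph of text and one column. The downside is that the composite answers a slightly different question, pain including the need for rescue, which is why both results are reported. The rescue rule is not changed.

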**11. b. Strategies to improve adherence to intervention protocol:**

- Face to face adherence reminder session, phone calls and text message reminders will take place to stress on the post-operative instructions to record postoperative pain levels.

**12. Outcomes:**

**Primary outcome:**

- **Antibacterial efficacy:** will be assessed by counting the number of colony forming units (CFU) before and after irrigation (S1 and S2) for each patient. Collected samples will be cultured in serial dilution on blood agar plates, incubated for 24 hours, and then the number of colony forming units (CFUs) will be counted per ml.

Outcome	Tool	Unit	Time
antibacterial efficacy	Number of CFUs 	Numerical data	Samples collected before and after preparation and transferred to the laboratory for immediate cultivation.

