#### **Formulated question:**

In necrotic mandibular posterior teeth, would irrigating the canals using either Nano chitosan, Chlorhexidine or a combination of Nano chitosan and Chlorhexidine versus Sodium Hypochlorite have different effects on canal disinfection and postoperative pain?

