An in vitro study in 2017 claimed that the combination of 2% Chlorhexidine and 2% Chitosan is as effective as NaOCl against *E. Faecalis* in biofilms.

Since within the scope of our search no study evaluated the antimicrobial effects of Nano chitosan, Chlorhexidine/Chitosan combination as possible natural irrigants to those of NaOCl for irrigation in-vivo.

The **Aim** of the current study is to compare the antimicrobial effects of Nano chitosan, chlorhexidine, and their combination to NaOCl in patients with necrotic mandibular Premolars.

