## **7. Objectives:**

### **- Research hypothesis:**

There is no difference in the antimicrobial efficacy among Nano chitosan, Chlorhexidine, Chlorhexidine/Nano Chitosan and Sodium hypochlorite in root canal treatment.

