### **- Primary objective:**

The primary objective of this study is to assess the antimicrobial efficacy of Nano-chitosan, chlorhexidine and Chlorhexidine/Nano Chitosan combination versus NaOCl.

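### The primary question is worded as irrigant efficacy without limit, but the arms differ only in a 5 ml final flush after shared 2.5% NaOCl preparation; the wording and the CFU analysis should match that contrast

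*Combined protocol and SAP*

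**What the plan says.** Section 12 defines the primary outcome as "counting the number of colony forming units (CFU) before and after irrigation (S1 and S2".

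The statements of what the trial is to learn carry no limit on how the solutions are used:

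- The formulated question asks "would irrigating the canals using either Nano chitosan, Chlorhexidine or a combination of Nano chitosan and Chlorhexidine versus Sodium Hypochlorite have different effects".
- The aim, at the end of the rationale, is to "compare the antimicrobial effects of Nano chitosan, chlorhexidine, and their combination to NaOCl".
- The research hypothesis in section 7 reads "There is no difference in the antimicrobial efficacy among Nano chitosan, Chlorhexidine, Chlorhexidine/Nano Chitosan and Sodium hypochlorite in root canal treatment".
- The primary objective is to "assess the antimicrobial efficacy of Nano-chitosan, chlorhexidine and Chlorhexidine/Nano Chitosan combination versus NaOCl".

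The hypothesis speaks of a difference among four solutions rather than of each against NaOCl, but it is just as unrestricted. Only the secondary (pain) objective carries the limit: its list of the four solutions ends "NaOCl as a final flush before obturation".

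Section 11.a gives the procedure. "The initial sample S1 will be collected from root canals before preparation". All groups then have the same rotary sequence, and "The canals will be thoroughly irrigated for 1 minute between every two subsequent files using 2 ml of 2.5% NaOCl". EDTA and saline follow in every canal. Only then does each arm receive its 5 ml flush of nano chitosan, chlorhexidine, the combination or 5.25% NaOCl. A 10 ml saline rinse and S2 come next.

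Section 20 plans ANOVA or Kruskal-Wallis across the four groups for numeric variables. It does not say whether the CFU quantity is S2, the change from S1 or a percentage reduction.

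**The concern.** A conclusion written straight from the hypothesis and the primary outcome would be broader than the design allows. The statement of the problem motivates the trial by the tissue irritation that NaOCl causes and looks for other solutions. Yet every canal in every arm is irrigated with NaOCl during preparation. A finding of no difference, or of superiority, could be read as evidence that nano chitosan or chlorhexidine can do the work of NaOCl in the canal. The trial will hold no evidence on that.

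The outcome label adds to the risk. The interval from S1 to S2 covers instrumentation, the shared NaOCl, EDTA and saline as well as the allocated flush. In the clinical trial of 2.5% NaOCl and 2% chlorhexidine summarised in the review of literature, the compared irrigant was used during rotary preparation, so the same two labels bracketed its whole use. Here they bracket much more than the allocated solution.

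The analysis gap is linked. Two counts are taken per patient, and the plan does not fix which quantity made from them answers the primary question.

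**Working it through.** **1. What separates the arms (section 11.a).**

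| Step | Same in all arms? |
|---|---|
| S1 | yes |
| Files #18, #20, #25, #35 | yes |
| 2.5% NaOCl between files | yes |
| EDTA, then saline | yes |
| 5 ml allocated flush | **no** |
| 10 ml saline | yes |
| S2 | yes |

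Four files give three intervals, so the shared step is 3 x 2 ml = 6 ml of 2.5% NaOCl over 3 x 1 = 3 minutes. No sample is planned between the end of the shared steps and the allocated flush. The between-arm contrast at S2 is therefore the final flush, given NaOCl preparation. The fall from S1 to S2 within an arm is preparation plus flush.

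**2. Where the limit is stated.** It is absent from the formulated question, the aim, the research hypothesis, the primary objective and the primary outcome. It is present in the pain objective and in the intervention text of section 11.a.

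**3. How S2 is timed.** Section 11.a places it after the flush and the saline rinse. The text of section 12 places S1 and S2 around irrigation, and its table places them around preparation. The time line in section 13 puts the second sample after cleaning and shaping and does not mention the flush.

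**4. The plan's own sample size (section 14).** Inputs: difference 75, SD 75, two-sided 5%, power 80%. The standardised difference is 75/75 = 1.0.

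- Normal approximation: 2 x (1.96 + 0.84)² / 1.0² = 15.7, so 16 per group.
- Two-sample t-test: 16.7, so 17 per group, with power 80.7% at 17.
- Allowance for losses: 17/20 = 0.85, an implied 15%.

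The stated 17 and 20 reproduce. They rest on raw counts compared between two groups without adjustment.

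**5. What the choice of CFU quantity does to precision.** The documents give no S1–S2 correlation r. Assume r = 0.3, 0.5 or 0.7, equal SDs on the log scale and no zero counts. Variance relative to S2 alone (1.00):

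| | formula | r = 0.3 | r = 0.5 | r = 0.7 |
|---|---|---|---|---|
| Change from S1 | 2(1 − r) | 1.40 | 1.00 | 0.60 |
| S2 adjusted for S1 | 1 − r² | 0.91 | 0.75 | 0.51 |

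Chance difference in mean S1 between two arms, 95% range: 1.96 x √(2/20) = ±0.62 SD with 20 per arm, and 1.96 x √(2/17) = ±0.67 SD with 17.

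**6. Are zeros likely at S2?** In the clinical trial cited in step 1's context, the review of literature reports 44% (NaOCl) and 40% (chlorhexidine) of canals still positive after preparation. So 100 − 44 = 56% and 100 − 40 = 60% were not. The assay was PCR, not culture, so this is only a pointer. It does mean that zeros should be expected and that step 5 is an illustration.

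**The case against.** The strongest reply is that nothing is hidden. Section 11.a says for each arm that the flush comes after preparation is complete, and the pain objective, directly below the primary one, calls it a final flush. Objectives are read together with interventions, and no passage says that a test solution replaces NaOCl during preparation. The in vitro study behind the combination arm also prepared its teeth with 5% NaOCl before applying the test irrigants, and it too spoke simply of irrigant efficacy. All of this stands, and it makes the point one of wording and analysis rather than of design. It does not remove it: the hypothesis and primary outcome define what will be concluded, and those are where the limit is missing.

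It is also fair to say that the unnamed CFU quantity is a separate matter from scope. The two meet because S2 adjusted for S1 is the quantity that isolates the tested contrast.

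A reader might infer several stronger things that the documents do not support:

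- *That the comparison is biased.* The preparation is common to all arms and allocation is random, so the between-arm contrast is sound for a final flush.
- *That the plan will credit the S1-to-S2 fall to the test solution.* Section 20 plans only comparisons between groups.
- *That the share of NaOCl given to the test arms measures how far the contrast is weakened.* Volume times concentration does not measure antimicrobial effect; the review of literature itself reports no significant difference between 1% and 6% NaOCl in vitro.
- *That power is lost.* The documents do not say how much of the assumed 75-unit difference would remain after shared preparation.
- *That S2 may be taken before the flush.* Section 11.a is clear; the other wordings are loose rather than false.

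**Conclusion.** The concern holds as a mismatch between the primary statements and the contrast tested. The trial can say how each solution compares with 5.25% NaOCl when used as a 5 ml final flush after common preparation with 2.5% NaOCl, EDTA and saline. It cannot say whether any of them could replace NaOCl as the main irrigant. This follows from the sequence in section 11.a and needs no assumption.

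The scope problem has no numerical size. The analysis gap has one only by illustration: relative variance of 0.91, 0.75 or 0.51 for S2 adjusted for S1, on an assumed r of 0.3, 0.5 or 0.7, equal log-scale SDs and no zeros. On those assumptions adjustment never does worse than S2 alone, while a change score does worse at r = 0.3. The randomised comparison is valid, the stated sample size reproduces on its own terms, and no bias or loss of power is claimed.

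**What to change.** 1. **Scope.** Restate the research hypothesis, the primary objective and the primary outcome, with the formulated question and aim to match, as the effect on bacterial count of each solution versus 5.25% NaOCl, used as a 5 ml final flush after common preparation with 2.5% NaOCl.
2. **Analysis.** In section 20, replace the unadjusted ANOVA or Kruskal-Wallis on an unnamed quantity with one prespecified between-arm comparison of S2 CFU/ml adjusted for S1. Use ANCOVA on log10(CFU+1) or, if zeros are expected, rank ANCOVA (Quade) as the single primary method. Choose before any counts are seen by arm, and do not allow a later switch because zeros turn out to be many.
3. **Timing.** Reconcile the sampling time in the section 12 table and the section 13 time line with section 11.a.

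Cost: a narrower claim and a small amount of extra analysis. S1 is already collected, so no patient, sample or procedure is added and the irrigation regimen is untouched. One consequence should be stated openly: section 14 is built on a raw-count difference of 75 with SD 75, so its 17 per group does not directly describe power on the log or rank scale.
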